Hypersensitivity reactions, including serious hypersensitivity reactions.	Serious hypersensitivity reactions including anaphylaxis have been reported in postmarketing experience with guselkumab in psoriasis patients.	 Participants with known allergy, hypersensitivity, or intolerance to guselkumab or its excipients will be excluded from the study. Sites are instructed that before any administration of study intervention, appropriately trained personnel and medications (eg, injectable epinephrine) must be available to treat hypersensitivity reactions, including anaphylaxis. In addition, all participants must be observed carefully for signs and symptoms of a hypersensitivity reaction (eg, urticaria, pruritis, angioedema, wheezing, dyspnea, or hypotension) (Section 8.2.8).
		• Any participant who develops a serious hypersensitivity reaction such as anaphylaxis must discontinue study intervention (Section 7.1).
Malignancy	The preponderance of preclinical data suggests that blockade of endogenous interleukin (IL)-23 would not be detrimental and may in fact be beneficial in tumor immunosurveillance and host protection; however, a risk of malignancy cannot be excluded.	 Those participants who currently have a malignancy or have a history of malignancy within 5 years prior to screening (with exceptions noted in Section 5.2) will be excluded from the study. Additionally, participants who have a history of lymphoproliferative disease, including lymphoma; a history of monoclonal gammopathy of undetermined significance or signs and symptoms suggestive of possible lymphoproliferative disease, such as lymphadenopathy or splenomegaly will be excluded from the study (Section 5.2). During the conduct of the study, participants will undergo regular clinical monitoring including routine safety laboratory tests to assess for any changes in health

Liver injury	A serious adverse event (SAE) of 'toxic hepatitis' was reported in the ongoing Phase 2/3 guselkumab	status that may indicate a possible malignancy. Participants who develop a malignancy during the study (with the exception of no more than 2 localized basal cell skin cancers that are treated with no evidence of recurrence or residual disease) will be discontinued from study intervention (Section 7.1). During the conduct of the study, liver function tests will be monitored at regular intervals in

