- The participant has a serious adverse reaction that is related to an injection or an infusion, including an injection-site or infusion reaction, resulting in bronchospasm with wheezing and/or dyspnea that requires ventilatory support OR that results in symptomatic hypotension with a decrease in systolic blood pressure >40 mm Hg.
- The participant has a reaction resulting in myalgia and/or arthralgia with fever and/or rash (suggestive of serum sickness and not representative of signs and symptoms of other recognized clinical syndromes) occurring 1 to 14 days after an injection of study intervention. These may be accompanied by other events including pruritus, facial, hand, or lip edema, dysphagia, urticaria, sore throat, and/or headache.
- The participant has severe liver test abnormalities that are not transient and are not explained by other etiologies. Such abnormalities would include (see Section 10.6, Appendix 6: Liver Safety: Suggested Actions and Follow-up Assessments):

Alanine aminotransferase (ALT) or aspartate aminotransferase (AST) $\geq 5 \times \text{ULN}$.

ALT or AST \geq 3 × ULN for more than 4 weeks.

ALT or AST $\ge 3 \times ULN$ and cannot be monitored weekly for 4 weeks.

ALT or AST \ge 3 × ULN and TBL \ge 2 × ULN or international normalized ratio [INR] >1.5 (INR not acceptable for participants on anticoagulants).

ALT or AST $\ge 3 \times$ ULN and symptoms (new or worsening) believed to be related to liver injury (such as fatigue, nausea, vomiting, right upper quadrant pain or tenderness, or jaundice) or hypersensitivity (such as fever, rash or eosinophilia).

• The participant has a malignancy including squamous cell skin cancer. Consideration may be given to allowing participants who develop ≤2 basal cell skin cancers that are adequately treated with no evidence of residual disease to continue to receive study intervention.

Discontinuation of a participant's study intervention must be strongly considered under the following conditions:

- The participant develops a serious infection, including but not limited to sepsis or pneumonia.
- The participant develops a severe injection-site or infusion reaction.

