8.2.6. Adverse Events Temporally Associated with Infusion

Any AE (except laboratory abnormalities) that occurs during or within 1 hour after the IV infusion of study intervention will be carefully evaluated. Minor infusion-related AEs may be managed by slowing the rate of the IV infusion and/or treating with antihistamines and/or acetaminophen (paracetamol) as clinically indicated. If an IV infusion of study intervention is stopped because of an AE that, in the opinion of the investigator, is not severe or does not result in a SAE, the infusion may be restarted with caution.

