8.2.7. Injection-site Reactions

An injection-site reaction is any adverse reaction at a SC study intervention injection site. Injection sites will be evaluated for reactions and any injection-site reaction will be recorded as an AE.

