8.2.8. Hypersensitivity Reactions

Before any SC injection or IV infusion, appropriately trained personnel and medications must be available to treat hypersensitivity reactions, including anaphylaxis. All participants must be observed carefully for symptoms of a hypersensitivity reaction (eg, urticaria, itching, hives). If a

mild or moderate hypersensitivity reaction is observed, acetaminophen, nonsteroidal anti-inflammatory drugs, and/or diphenhydramine may be administered.

In the case of a severe hypersensitivity reaction (eg, anaphylaxis), SC aqueous epinephrine, corticosteroids, respiratory assistance, and other proper resuscitative measures are essential and must be available at the study site where the injections or infusions are being administered.

Participants who experience serious adverse reactions related to an injection or infusion should be discontinued from further study intervention administrations.

Participants who experience reactions following an injection or infusion that result in bronchospasm with wheezing and/or dyspnea that requires ventilatory support, or symptomatic hypotension with a decrease in systolic blood pressure greater than 40 mm Hg will not be permitted to receive additional study intervention.

Participants who experience reactions suggestive of serum sickness-like reactions (resulting in symptoms such as myalgia and/or arthralgia with fever and/or rash that are not representative of signs and symptoms of other recognized clinical syndromes) occurring 1 to 14 days after an injection of study intervention, should be discontinued from further study intervention administrations. Note that these symptoms may be accompanied by other events including pruritus, facial, hand, or lip edema, dysphagia, urticaria, sore throat, and/or headache.

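### Protocol 7.1 is narrower than the anaphylaxis stop that 2.3.1 cites it for, and the 8.2.6 restart rule can conflict with 8.2.8

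*Protocol*

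**What the plan says.** **Section 2.3.1**, hypersensitivity row of the risk table: "Any participant who develops a serious hypersensitivity reaction such as anaphylaxis must discontinue study intervention (Section 7.1").

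**Section 7.1**, mandatory list. One bullet deals with acute reactions. It requires "a serious adverse reaction that is related to an injection or an infusion, including an injection-site or infusion reaction, resulting in bronchospasm" and goes on to specify wheezing and/or dyspnea needing ventilatory support, or alternatively symptomatic hypotension with a systolic fall of more than 40 mm Hg. The same list has a bullet on serum-sickness-like reactions after an injection, and one that applies when the investigator believes stopping is in the participant's best interest for safety or tolerability reasons.

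**Section 7.1**, weaker list, where stopping is only to be strongly considered: "The participant develops a severe injection-site or infusion reaction".

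**Section 8.2.8** introduces emergency treatment with "In the case of a severe hypersensitivity reaction (eg, anaphylaxis"). It then gives two stop rules for acute reactions. The first rests on seriousness: "Participants who experience serious adverse reactions related to an injection or infusion should be discontinued from further study intervention administrations". The second rests on the same two clinical features as 7.1, with no seriousness condition. Its hypotension limb reads "symptomatic hypotension with a decrease in systolic blood pressure greater than 40 mm Hg will not be permitted to receive additional study intervention".

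**Section 8.2.6**, on an infusion that was stopped because of an AE, allows restart if the AE "in the opinion of the investigator, is not severe or does not result in a SAE, the infusion may be restarted with caution".

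**The concern.** Section 7.1 is the list of mandatory stops and the place to which 2.3.1 sends the reader. If it is narrower than 2.3.1 and 8.2.8, two sites could treat the same reaction differently depending on which section they open: one ends treatment, the other gives the next dose after discretionary review. The restart rule raises the same problem during a single infusion, because 8.2.6 neither refers to 8.2.8 nor makes an exception for it.

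The setting makes this more than editorial. Section 2.3.1 reports serious hypersensitivity, including anaphylaxis, from postmarketing use in psoriasis. Each participant is scheduled for three infusions and then SC doses every four weeks from Week 12 to Week 48. Everyone in the extension has infusions again at Weeks 52, 56 and 60, and some SC doses may be given at home at Weeks 84, 92 and 100. What is at stake is participant safety and uniform conduct, not inference.

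**Working it through.** The plan gives no figure on this point and no arithmetic beyond counting applies. The check sets the sections side by side.

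**Step 1: how the 7.1 bullet parses.** On the natural reading, the two features restrict the bullet: the reaction must be serious *and* have a listed feature. If every serious reaction already counted, naming the features would be redundant. On the alternative reading, the features belong to the examples after the word *including*, so any serious injection or infusion reaction is a mandatory stop. The text does not settle which applies.

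**Step 2: acute reactions against each section.** A listed feature means bronchospasm or dyspnea needing ventilatory support, or symptomatic hypotension with a systolic fall above 40 mm Hg.

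| Reaction | 2.3.1 | 8.2.8 | 7.1, natural reading | 7.1, alternative reading |
|---|---|---|---|---|
| Serious, listed feature | must stop if hypersensitivity | barred | must stop | must stop |
| Serious anaphylaxis, no listed feature | must stop | should stop | strongly considered if a severe infusion reaction; otherwise investigator judgement | must stop |
| Non-serious, listed feature | not addressed | barred | not in the acute-reaction bullet | not in the acute-reaction bullet |

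An example of the second row is serious anaphylaxis with urticaria, angioedema and wheeze, treated with epinephrine, without ventilatory support or the stated pressure fall. After an infusion it reaches the strongly-considered list, because 8.2.8 treats anaphylaxis as an example of a severe reaction. After an SC dose that item does not fit a systemic reaction, since "An injection-site reaction is any adverse reaction at a SC study intervention injection site" (8.2.7), so the investigator-judgement bullet is what remains.

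The third row is nearly empty for the respiratory feature. A reaction needing ventilatory support would ordinarily be serious under 10.4.1 as life-threatening or medically important. In practice the row is a symptomatic systolic fall above 40 mm Hg judged non-serious.

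**Step 3: the restart rule.** Severity (10.4.3) and seriousness (10.4.1) are separate scales. Hospitalization, for example, makes an event serious whatever its grade. That gives four combinations.

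| AE | 8.2.6, literal *or* | 8.2.6, read as *neither* | 8.2.8 seriousness rule | 8.2.8 feature bar |
|---|---|---|---|---|
| Not severe, not serious | restart allowed | restart allowed | does not apply | applies if feature present |
| Not severe, serious | restart allowed | no restart | should stop | applies if feature present |
| Severe, not serious | restart allowed | no restart | does not apply | applies if feature present |
| Severe, serious | no restart | no restart | should stop | applies if feature present |

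- Literal reading: restart is open in 3 of 4 combinations. Of the 2 serious ones, 1 (not severe) may be restarted although 8.2.8 says it should stop. The feature bar applies to all 4, and 3 of those are open to restart.
- *Neither* reading: restart is open in 1 of 4. The conflict with the seriousness rule disappears. The only overlap left is a listed feature judged neither severe nor serious, in practice the hypotension case. That is 1 narrow case, or 0 if every such fall is classed as serious under 10.4.1, which the protocol leaves to judgement.

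**The case against.** The strongest reply is that the stops already exist in binding text. Section 2.3.1 says *must*, and 8.2.8, the section headed for hypersensitivity and the natural place to look, both tells sites to stop after serious reactions and bars further drug after the listed features. A reader might infer that the protocol has no anaphylaxis stop; it does, and that inference fails.

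Section 7.1 also has a mandatory route through the investigator's safety judgement. Doses are four weeks apart and SAEs reach the sponsor within 24 hours, so a serious reaction would be known well before the next scheduled dose. This stands as mitigation. It does not make an event-triggered stop out of a judgement clause, and a 24-hour report comes too late to affect a restart in the same session.

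On 8.2.6, the sentence just before the restart rule concerns minor infusion events, the rule is permissive, and a site can satisfy both sections by not restarting. The intended meaning is probably *neither*. That is fair, and it is why the conflict is narrow on the sensible reading. But the restart sentence is not limited to minor events, and the connective as printed allows more than was probably meant.

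**Conclusion.** The point holds as an inconsistency between sections that should be corrected. Section 7.1 does not deliver, on its natural reading, the stop for which 2.3.1 cites it. The gap is serious anaphylaxis without either listed feature. It would largely close under the alternative parse, but a mandatory stop should not depend on the parse. The added seriousness condition matters in practice only for a symptomatic systolic fall above 40 mm Hg judged non-serious, and that remains under both parses. The restart rule conflicts with 8.2.8 for serious, non-severe reactions if read literally, and in 0 to 1 narrow cases if read as *neither*.

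Two stronger readings are not supported. A reader might infer that systemic reactions after an SC dose fall outside 7.1 altogether. They do not: the mandatory bullet covers serious injection-related reactions with a listed feature, and the next bullet covers serum-sickness-like reactions. A reader might also infer that 7.1 captures none of the stops stated elsewhere. That depends on one parse and ignores that 7.1 does cover serious reactions with the listed features, the gravest cases.

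The documents give no rate for anaphylaxis or infusion hypotension in this population, so no expected number of participants is claimed. The estimands, sample size and primary analysis are unaffected.

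**What to change.** 1. In 7.1, add a mandatory stop for any serious hypersensitivity reaction, including anaphylaxis. Remove the seriousness condition for reactions with either listed feature, so that the bullet matches 8.2.8.
2. In 8.2.6, allow restart only if the AE is not severe *and* does not result in an SAE *and* meets no stopping criterion in 7.1 or 8.2.8.

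The cost is a protocol wording amendment and site notification, with no new assessments. The downside is possibly a few more discontinuations.

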	Crohn's disease program in a participant who received guselkumab 1200 mg intravenous (IV) at Weeks 0, 4, and 8, and 200 mg subcutaneous (SC) at Week 12. Based on the hepatocellular pattern of injury, temporal relationship of the event to guselkumab exposure, and the exclusion of alternative etiologies, this event may represent druginduced liver injury possibly related to guselkumab. Alanine aminotransferase (ALT)/ aspartate aminotransferase AST abnormailities are a known risk for guselkumab, and that in the psoriatic arthritis studies, patients receiving guselkumab every 4 weeks (Q4W) were more likely to experience transaminase elevations than those receiving it every 8 weeks (Q8W).	accordance with regulatory guidance (FDA 2009). In addition, the induction doses evaluated in this clinical program will not exceed 400 mg IV. • Participants with marked liver enzyme elevations or symptoms or signs of liver dysfunction (eg, jaundice), should undergo a thorough investigation for possible causes of liver injury. A participant must have their study intervention discontinued if the participant has severe liver test abnormalities that are not transient and are not explained by other etiologies (Section 7.1 and Section 10.6).
Immunosuppression	It is unknown if guselkumab in combination with other immunosuppressives increases the risk of diseases associated with immunosuppression, such as infections or malignancy.	• In order to minimize the theoretical increased risk of infection or malignancy with the combination of guselkumab with immunosuppressive therapy, the baseline dose of oral corticosteroids on study entry is limited ≤10 mg of prednisolone or equivalent per day which must be at a stable dose ≥4 weeks prior to first dose of study intervention. Furthermore, participants receiving investigational or approved immunomodulatory agents like IL-23 inhibitor therapy, IL-12/23 inhibitors, or IL-17 inhibitors, failed for efficacy in SSc or within 12 weeks or 5 half-lives

CONFIDENTIAL – FOIA Exemptions Apply in U.S.

27

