7.1.1. Liver Chemistry Stopping Criteria

Discontinuation of study intervention for abnormal liver tests is required by the investigator when a participant meets 1 of the conditions outlined in Section 10.6, Appendix 6: Liver Safety: Suggested Actions and Follow-up Assessments, or in the presence of abnormal liver chemistries not meeting protocol-specified stopping rules if the investigator believes that it is in best interest of the participant.

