Serious adverse events, including those spontaneously reported to the investigator within 12 weeks after the last dose of study intervention, must be reported. The sponsor will evaluate any safety information that is spontaneously reported by an investigator beyond the time frame specified in the protocol. Possible Hy's law case (AST or ALT \geq 3 x ULN together with total bilirubin \geq 2 x ULN or INR > 1.5) is considered an important medical event and must be reported to the sponsor in an expedited manner using the Serious Adverse Event Form, even before all other possible causes of liver injury have been excluded. (INR criterion is not applicable to participants receiving anticoagulants.)

Information regarding SAEs will be transmitted to the sponsor using the Serious Adverse Event Form, which must be completed and signed by a physician from the study site, and transmitted to the sponsor within 24 hours. The initial and follow-up reports of an SAE should be made by facsimile (fax). Telephone reporting should be the exception and the reporter should be asked to complete the appropriate form(s) first.

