10.6. Appendix 6: Liver Safety: Suggested Actions and Follow-up Assessments

A. STOPPING ALGORITHM

Study intervention will be discontinued for a participant if liver chemistry stopping criteria are met.

Phase 2 Liver Chemistry Stopping Criteria and Increased Monitoring Algorithm

Abbreviations: ALT = alanine transaminase; AST = aspartate transaminase, INR = international normalized ratio; SAE = serious adverse event; ULN = upper limit of normal, Tbili = Total bilirubin.

B. FOLLOW-UP ASSESSMENTS

Phase 2 liver chemistry stopping criteria are designed to assure participant safety and to evaluate liver event etiology.

Phase 2 Liver Chemistry Stopping Criteria and Follow-up Assessments

Liver Chemistry Stopping Criteria and Fonow-up Assessments				
4 T FD 4 GFD	Liver Chemistry Stopping Criteria			
ALT or AST- absolute	ALT or AST ≥5xULN			
ALT or AST	ALT on ACT >2 will Ni nomicto fon >4 woods			
Increase	ALT or AST ≥3xULN persists for ≥4 weeks			
Bilirubin ^{1,2}	ALT or AST ≥3xULN and to	otal bilirubin ≥2xULN (>35% direct bilirubin)		
INR ²	ALT or AST ≥3xULN and in	nternational normalized ratio (INR) >1.5		
Cannot Monitor	ALT or AST≥3xULN and ca	nnot be monitored weekly for 4 weeks		
Symptomatic ³	ALT or AST ≥3xULN assoc	iated with symptoms (new or worsening)		
	believed to be related to liver	r injury or hypersensitivity		
Su	ggested Actions, Monitoring	, and Follow-up Assessments		
	Actions	Follow-up Assessments		
• Immediately di	scontinue study intervention	• Viral hepatitis serology ⁴		
24 hours	t to the sponsor within	• Obtain blood sample for pharmacokinetic (PK) analysis approximately 60 minutes after the most recent dose ⁵		
 Complete the liver event/expedited reporting form, and complete an SAE CRF if the event also met the criteria for an SAE² Perform follow-up assessments as described in the Follow-up Assessment column. 		Obtain serum creatine phosphokinase (CPK), lactate dehydrogenase (LDH), gamma-glutamyltransferase (GGT), glutamate dehydrogenase (GLDH), and serum albumin		
Monitor the participant until liver chemistry test abnormalities resolve, stabilize, or return to baseline		 Fractionate bilirubin, if total bilirubin ≥2xULN 		
MONITORING:		Obtain complete blood count with		
If ALT or AST ≥3	SXULN AND total bilirubin	differential to assess eosinophilia		

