- Serum bilirubin fractionation should be performed if testing is available. If serum bilirubin fractionation is not immediately available, discontinue study intervention if ALT or AST ≥3xULN and total bilirubin ≥2xULN. Additionally, if serum bilirubin fractionation testing is unavailable, record the absence/presence of detectable urinary bilirubin on dipstick which is indicative of direct bilirubin elevations suggesting liver injury.
- 2. All events of ALT or AST ≥3xULN and total bilirubin ≥2xULN (>35% direct bilirubin) or ALT or AST ≥3xULN and INR >1.5 may indicate severe liver injury (possible 'Hy's Law') and must be reported to sponsor in an expedited manner and as an SAE if SAE criteria met (excluding studies of hepatic impairment or cirrhosis). The INR stated threshold value will not apply to participants receiving anticoagulants.
- 3. New or worsening symptoms believed to be related to liver injury (such as fatigue, nausea, vomiting, right upper quadrant pain or tenderness, or jaundice) or hypersensitivity (such as fever, rash or eosinophilia).
- 4. Includes HBsAg (HBV surface antigen), anti-HBs (HBV surface antibody), and anti-HBc total (HBV core antibody total). For participants who are eligible with negative HBsAg, and positive core antibody (anti-HBc) and/or surface antibody (anti-HBs), and negative HBV DNA test, HBV DNA quantitation should be monitored at least every 3 months or shorter.

5. PK sample may not be required for participants known to be receiving placebo or non-comparator interventions. Record the date/time of the PK blood sample draw and the date/time of the last dose of study intervention prior to the blood sample draw on the CRF. If the date or time of the last dose is unclear, provide the participant's best approximation. If the date/time of the last dose cannot be approximated OR a PK sample cannot be collected in the time period indicated above, do not obtain a PK sample. Instructions for sample handling and shipping are in the Investigational Product Procedures Manual (IPPM) and Investigational Product Procedure Instructions (IPPI).

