5.7.3. Additional Safety Assessments

5.7.3.1. Clinical Laboratory Tests

Clinical laboratory tests will be displayed for the participants included in the safety analysis set.

Descriptive statistics will be presented for selected chemistry, hematology, and urinalysis (pH and specific gravity) laboratory tests at scheduled time points.

Change from baseline over time through Week 52 will be summarized for selected chemistry, hematology, and urinalysis (pH, and specific gravity) tests and displayed by intervention group. A box plot of change from baseline over time through Week 52 will be provided for the following laboratory tests: hematology: hemoglobin, platelets, total WBC, absolute lymphocytes, and absolute neutrophils; chemistry: ALT, AST, Alkaline phosphatase and total bilirubin.

Applicable lab results are to be graded based on National Cancer Institute Common Terminology Criteria for Adverse Events (NCI-CTCAE) version 5.0. The laboratory tests not included in the NCI-CTCAE criteria will not be presented in the corresponding tables or listings.

Summary of maximum postbaseline NCI-CTCAE toxicity grade through Week 52 will be presented. Additionally, shift table from baseline laboratory value to the worst toxicity grade through Week 52 in chemistry and hematology tests with NCI-CTCAE will be summarized for the following lab parameters: hematology: hemoglobin, platelets, total WBC, absolute lymphocytes, and absolute neutrophils; chemistry: ALT, AST, Alkaline phosphatase and total bilirubin.

Proportion of participants with maximum postbaseline ALT and AST through Week 52 will be provided for the categories:

- >1 to ≤ 3 x ULN
- >3 to ≤ 5 x ULN
- >5 to ≤ 10 x ULN
- >10 to ≤ 20 x ULN
- >20 x ULN

Besides, proportion of participants with total bilirubin >2 x ULN and either AST or ALT ≥ 3 x ULN at the same timepoint will also be provided.

In addition, proportion of participants with maximum postbaseline alkaline phosphatase through Week 52 will be provided for the categories:

- ≤ 1 x ULN
- >1 to ≤ 1.5 x ULN
- >1.5 to ≤ 2.5 x ULN
- >2.5 to ≤ 5 x ULN
- >5 to ≤ 20 x ULN
- >20 x ULN

Above analysis will also be summarized through LTE period.

Listings of participants with any abnormal postbaseline laboratory values of NCI-CTCAE grade ≥ 2 or any abnormal postbaseline laboratory values of reference range will also be provided.

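### The mandatory liver stopping rule is worded differently in Protocol 7.1 and in Protocol 7.1.1 and 10.6, so identical values can require a stop under one section and not under another

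*Protocol*

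**What the plan says.** **Stopping.** Protocol 7.1 lists among its compulsory reasons for discontinuation: "The participant has severe liver test abnormalities that are not transient and are not explained by other etiologies". Its examples include ALT or AST at or above 3 x ULN for longer than 4 weeks, and the same elevation with total bilirubin at or above 2 x ULN, with no condition on the direct fraction. The risk table in 2.3.1 repeats the limit and cites both sections for it: "not transient and are not explained by other etiologies (Section 7.1 and Section 10.6".

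Section 7.1.1 says that discontinuation "is required by the investigator when a participant meets 1 of the conditions outlined in Section 10.6". Section 10.6 says: "Study intervention will be discontinued for a participant if liver chemistry stopping criteria are met". Its criteria table has "ALT or AST ≥3xULN persists for ≥4 weeks", and its bilirubin criterion needs more than 35% direct bilirubin. Footnote 1 waives that fraction only where fractionation cannot be had straight away.

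**Reporting.** Under 8.3.1, a possible Hy's law case "is considered an important medical event and must be reported to the sponsor in an expedited manner using the Serious Adverse Event Form", without waiting for other causes to be ruled out and with no direct-fraction condition. Under footnote 2 of 10.6, where the bilirubin limb needs more than 35% direct, such events "must be reported to sponsor in an expedited manner and as an SAE if SAE criteria met".

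**Tabulation.** SAP 5.7.3.1 gives the "proportion of participants with total bilirubin >2 x ULN and either AST or ALT" at or above 3 x ULN at the same timepoint.

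**The concern.** The protocol names liver injury as a risk. Section 2.3.1 cites a possible drug-induced case at a higher intravenous dose, and more transaminase elevations with 4-weekly than 8-weekly dosing in psoriatic arthritis. Maintenance dosing in this trial is 4-weekly. A compulsory stopping rule for a named risk should give one answer for one set of laboratory values.

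If it does not, sites that rely on different sections can reach different conclusions about whether a stop is compulsory. That bears first on consistent protection of participants. It also reaches planned outputs: SAP 5.2 summarises discontinuations of study intervention with reasons, SAP 5.7.2 summarises adverse events leading to discontinuation, and serious adverse events are part of a secondary endpoint.

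**Working it through.** No figure in the plan needs reproducing. The check sets the current texts side by side and runs illustrative cases through each rule.

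| Element | Section 7.1 | Sections 7.1.1 and 10.6 |
|---|---|---|
| Qualifier | Not transient and no other cause (also in 2.3.1) | None |
| Duration of ALT or AST ≥3 x ULN | >4 weeks | ≥4 weeks |
| Bilirubin limb | Total ≥2 x ULN | Total ≥2 x ULN and direct >35%, unless fractionation is not at hand |
| ALT or AST ≥5 x ULN; INR >1.5; symptoms; no weekly monitoring | Listed | Listed, same thresholds |

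**Case A.** ALT 6 x ULN with another identified cause.
- 7.1: 6 ≥ 5, but the qualifier fails. No mandatory stop.
- 10.6: 6 ≥ 5. Mandatory stop.

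**Case B.** ALT 3.5 x ULN for exactly 4 weeks, unexplained, no symptoms, monitored weekly, bilirubin and INR normal.
- 7.1: 4 > 4 is false. No mandatory stop.
- 10.6: 4 ≥ 4 is true. Mandatory stop.

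**Case C.** ALT 3.5 x ULN, total bilirubin 2.2 x ULN, measured direct fraction 25%, INR normal, no symptoms, monitored weekly, unexplained and persisting but for under 4 weeks.
- 7.1: 3.5 ≥ 3, 2.2 ≥ 2 and the qualifier is met. Mandatory stop.
- 10.6: 25% > 35% is false, 3.5 < 5, duration is under 4 weeks, and the INR, symptom and monitoring criteria are not met. No mandatory stop.

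Sections 7.1.1 and 10.6 are wider in A and B; 7.1 is wider in C. Neither is simply the stricter rule.

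**Reporting.** For case C, 8.3.1 requires the Serious Adverse Event Form; footnote 2 of 10.6 is not triggered. If the direct fraction were 50%, 8.3.1 would still require the form outright, while footnote 2 would require expedited reporting but serious-event reporting only conditionally.

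**Bilirubin boundary.** At exactly 2 x ULN, 2 ≥ 2 holds in 7.1, 8.3.1 and 10.6 alike. Only the SAP table differs, since 2 > 2 is false.

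**Scale.** With 28 participants planned per arm, one participant is 1/28 = 0.036, about 3.6 percentage points in any by-arm safety proportion. The documents give no expected rate of liver events, so the number affected cannot be estimated.

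**The case against.** The strongest reply is that 7.1 and 7.1.1 are both compulsory, that 7.1.1 is a subsection of 7.1, and that 7.1 itself points to 10.6. A site must obey both, so meeting either set of criteria means a stop, and silence in one section is not a contrary order. Section 10.6 also bars restarting unless the protocol allows it and the sponsor approves, which fits a reading of stopping first and establishing the cause afterwards.

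Part of this stands. These are not opposing orders, and both 7.1 and 7.1.1 leave the investigator free to stop. A reader might infer that some section directs a participant to be kept on treatment; none does.

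But the protocol nowhere says that the sections combine in this way. That reading would leave the 7.1 qualifier without effect wherever a 10.6 criterion is met, and the direct-fraction condition without effect in case C. The risk table points the other way, since it cites 10.6 as a source for the qualified rule.

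On reporting, a reader might infer that a possible Hy's law case could escape serious-event reporting. The documents largely answer this: 8.3.1 designates such a case as medically important, 10.4.1 lists that among the seriousness criteria, and 8.3.1 requires the form in its own right. What remains is the differing bilirubin definition and a condition in 10.6 that 8.3.1 makes redundant.

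A reader might also fault the SAP table for having no INR limb. INR is not in the routine laboratory panel in 10.2 and is asked for in the liver-event work-up, so its absence from a descriptive table is not an error.

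**Conclusion.** The point holds as an inconsistency in current protocol text on three elements of the stopping rule: the qualifier, the duration and the direct-bilirubin condition. Case A shows that it goes beyond values lying exactly on a limit. The Hy's law difference is secondary and concerns reporting, not stopping. The bilirubin inequality is a difference between SAP and protocol only; it does not support a claim that the protocol itself classifies a bilirubin of exactly 2 x ULN in two ways.

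No effect on the primary analysis is shown. A stop for liver values is not in itself an intercurrent event under SAP 5.3.2. The case for acting rests on a contradictory mandatory safety rule for a risk that the protocol names.

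The conclusion assumes that no precedence between sections is stated elsewhere. It rests on the text and tables of 10.6; the algorithm figure there was not available and was not relied on. The case values are illustrative.

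**What to change.** Reconcile Protocol 2.3.1, 7.1, 7.1.1, 8.3.1 and 10.6, including its footnotes and algorithm figure. Each of the following should then read the same throughout: the qualifier on transience and cause, the duration, the bilirubin condition, and the serious-event reporting of possible Hy's law cases. Alternatively, state which section governs. The choice of wording belongs to the sponsor's clinical team.

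In SAP 5.7.3.1, align the bilirubin inequality with the protocol's (at or above 2 x ULN), or explain the difference.

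The cost is protocol wording and one SAP line. Reconciling the text needs no change to the sample size or the primary analysis.
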